13	Time to haze	The subject's "time to haze" will be determined at 1m distance with the study lenses. First, the subject's psychophysical contrast threshold will be determined using a computerized chart. "Time to haze" will then be measured at 1 level above threshold. Directly after, the subject's required "time to clear" will be determined by counting blinks until the subject has cleared the haze. See Section 16.2.	Time to haze

14	Lens Removal	
Study lenses are removed from the eyes and placed into paper cups filled with saline. The sub-investigator will take the paper cups to a research assistant, who will determine if the lenses need replacement (in case of ACUVUE OASYS® with HYDRACLEAR® PLUS) or remain the same (in case of ULTRA™ with MoistureSeal™), depending on the randomization schedule. After the biomicroscopy exam (see next item) has been completed, the study lenses will be dispensed by a research assistant. Please see section 4.5 for details on lens dispense and maintaining masking.
 
In case of a product defect (e.g. lens edge tear), study lens(es) will be retained and returned to the sponsor, and a product complaint form will be completed in BioClinica. In case of a corneal adverse event, study lens(es) will be retained and analyzed at the CCLR.
	Lens Removal Lens information (If applicable)
15	Efron Biomicroscopy	The Efron slit lamp classification scale will be used to grade the findings. This includes corneal and conjunctival staining measurements with fluorescein (Section 16.2).	Biomicroscopy
16	Eye Rinse (if applicable)	The study investigator or technician will rinse the subject's eyes thoroughly with saline. The subject is asked to insert the study lenses.	Eye Rinse
17	CLUE and MRD questionnaire	The subject will complete the CLUE and MRD questionnaire using the BioClinica kiosk to evaluate the study lenses (Section 16.1).	CLUE and MRD questionnaire
18	Exit logMAR Visual Acuity	Distance visual acuity will be measured for each eye with the subject's spectacle correction or study lenses in place. The acuity will be recorded to the nearest letter OD, OS, and OU (Section 16.2).	Exit Visual Acuity
19	Subject Instructions	
Subjects will be instructed:
 
 • to wear their study lenses for a minimum of 5 days/week for 8 hours/day, while using digital devices. • to only use the provided study lenses and study solution (habitual spectacle use is permitted, but no other lens brand/kind). • to attend the Day 28 follow-up with their study lenses, having worn them for at least 6 hours while using digital devices. • to return their study solution bottle and lens case at the Day 28 visit. • to bring their habitual spectacles to the Day 28 visit. 	Instructions

Visit 9: Treatment 2 – Day 28 Follow-Up

VISIT 9: Treatment 2 – Day 28 Follow-Up			
Step	Descriptor	Details	CRF
The subject attends the visit wearing the study CLs, after having worn them for at least 6 hours while using digital devices.			
1	Changes in Concomitant Medications, Medical History and Adverse Events	Record any changes in concomitant medications and any adverse events that may have occurred since the last scheduled study visit.	Concomitant Medications Medical History Adverse Events (if applicable)
2	Collection of Study Solutions	The site staff will collect the solution bottle and case used to clean the study lenses.	Solution Collection
3	Subject Wear Time	Average wear time and comfortable wear time with the study lenses will be recorded.	Wear Time
4	Compliance	Subject compliance with wearing the study lenses will be recorded.	Compliance
5	Subject Reported Digital Device Use (Study Lens 2)	Subjects answer questions about their digital device use (duration while using digital devices, purpose etc.).	Subject Reported Digital Device Use
6	CLDEQ 8, MRD & CLUE questionnaires	The subject will complete the CLDEQ8, MRD and CLUE questionnaire using the BioClinica kiosk to evaluate the study lenses while using digital devices (Section 16.1).	Questionnaire
7	Unscheduled Lens Replacements	Any unscheduled lens replacements will be recorded (e.g. if subject tears lens while insert and more than two lenses are used/day as a result).	Unscheduled Lens Replacement
8	Non-invasive tear break-up time (NITBUT)	The subject's non-invasive tear break-up time (NITBUT) will be assessed. Three measurements for each eye will be performed while the subject is wearing the study lenses (pre-lens NITBUT). See section 16.2	NITBUT
9	Contact Lens Wettability	The front surface wettability of the study lens will be graded at the slit lamp biomicroscope. The wettability will be graded from 0 (excellent) to 4 (severely reduced), in 0.25 steps. See Section 16.2.	CL Wettability

10	Lens Fit Assessment	
Evaluate and grade lens centration, primary gaze movement, upgaze movement and tightness (push-up test).
 
An unacceptable lens fit will be any one or more of the following:
 
 • presence of limbal exposure (appearance of clear cornea) in any gaze • presence of edge lift • presence of unacceptable movement (excessive or insufficient) in all three movement categories (primary gaze, upgaze, and push-up). 
Note: If either lens is deemed unacceptable, the subject will not be able continue participation in the study (Section 16.2).
	Lens Fit Assessment
11	Lens Surface Evaluation	Grading Scale (Section 16.2) will be used to grade the front and back surface deposits.	Debris and Deposits
12	Distance and Near logMAR HCVA and LCVA	The subject's distance and near logMAR visual acuity will be determined with high (HCVA) and low contrast (LCVA) letter charts with the study lenses. The acuity will be recorded to the nearest letter for OD, OS and OU. See section 16.2.	Distance and Near logMAR HCVA and LCVA
13	Near Contrast Sensitivity	The subject's contrast sensitivity will be tested at near using Mars Letter Contrast Sensitivity Test Cards with the study lenses. The subject's contrast sensitivity will be recorded to the nearest letter for OU, in 0.04 log unit incremental steps. See Section 16.2.	Near Contrast Sensitivity
14	Time to haze	The subject's "time to haze" will be determined at 1m distance with the study lenses. First, the subject's psychophysical contrast threshold will be determined using a computerized chart. "Time to haze" will then be measured at 1 level above threshold. Directly after, the subject's required "time to clear" will be determined by counting blinks until the subject has cleared the haze. See Section 16.2.	Time to haze
15	Lens Removal	
Study lenses are removed from the eyes and are disposed of at the CCLR.
 
In case of a product defect (e.g. lens edge tear), study lens (es) will be retained and returned to the sponsor, and a product complaint form will be completed in BioClinica. In case of a corneal adverse event, study lens(es) will be retained and analyzed at the CCLR.
	Lens Removal
16	Efron Biomicroscopy	The Efron slit lamp classification scale will be used to grade the findings. This includes corneal and conjunctival staining measurements with fluorescein (Section 16.2).	Biomicroscopy
17	Eye Rinse (if applicable)	The study investigator or technician will rinse the subject's eyes thoroughly with saline.	Eye Rinse

FINAL EVALUATION			
Step	Descriptor	Details	CRF
1	Exit logMAR Visual Acuity	Distance visual acuity will be measured for each eye with the subject's spectacle correction in place. The acuity will be recorded to the nearest letter OD, OS, and OU (Section 16.2).	Exit Visual Acuity
2	Final Evaluation Form	Indicate if the subject completed the study successfully or not. If the subject discontinued, indicate the reason.	Subject Disposition
3	Protocol Deviations	Ensure any deviations that have been reported to the Sponsor have been recorded in the appropriate form.	Protocol Deviations Prompt Protocol Deviations

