- To compare the difference between total time of device use and comfortable wear time on a typical day when these subjects are wearing ACUVUE OASYS® and ULTRA™ silicone hydrogel lenses.

Study Design: This study is a group sequential, adaptive, prospective, single (subject)-masked, randomized, 2x2 cross-over dispensing design. After eligibility for the study has been confirmed during the screening visit, eligible subjects will wear each of the study lenses (ACUVUE OASYS® with HYDRACLEAR® PLUS, ULTRA™ with MoistureSeal™ Technology) for four weeks, in accordance with manufacturers' guidelines, with the order of lens wear being randomized.

Sample Size: Approximately 135 subjects will be enrolled to target completion of 80 subjects. An interim analysis will dictate if additional subjects will be enrolled to reach a maximum of 250 subjects. A maximum of 250 enrolled subjects was considered to account for any discontinuations due to adverse events as seen in phase 1. The study enrolment will be stopped after 50 additional phase 2 subjects complete the final visit. At this time existing subjects will be allowed to complete the study.

Qualification, Dispensing and Follow-Up Procedures:

Screening (V1): Subjects will complete informed consent. Demographics and medical history will be reviewed. Subjects must meet all of the study eligibility criteria to continue in the study.

Lens Dispense visits (V2 & V6): Subjects will be randomized to wear each of the two lens types for a total of 4 weeks. Randomization will occur at V2, when subjects will be dispensed either 1 pair of ACUVUE OASYS® with HYDRACLEAR® PLUS or 1 pair of ULTRA™ contact lenses with MoistureSeal™ Technology, according to their randomization schedule. Subjects will be dispensed the other (second) lens type at the second dispense visit (V6).

Follow-up Visits: All volunteers will return to the clinic on Day 1, Day 14 (± 3 days) and Day 28 (± 3 days) during each of the two study periods (V3, V4, V5 & V7, V8, V9). Adverse event and concomitant medication will be reported, if applicable. Clinical assessments will be performed. Subjects will be asked to complete a questionnaire on their experience with the study lenses. At V4 or V8 (Day 14), depending on the randomization schedule, ACUVUE OASYS® CLs will be replaced with a new pair according to the manufacturer's guidelines after 14 days of wear, while the ULTRA™ CLs (4-week replacement) will not be exchanged.

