4.4 STUDY DESIGN, TIME AND EVENTS SCHEDULE, FLOWCHART

This is a group sequential, adaptive, prospective, single (subject)-masked, randomized, 2x2 cross-over, dispensing design study. After a screening visit to determine eligibility, subjects will return for the first study lens dispense visit after a required 24 hour no-lens wear washout period. If, for scheduling purposes, the washout duration needs to be longer than 24 hours, the subject will be allowed to wear their habitual contact lenses, except during the last 24 hours prior to the next study visit, when only habitual spectacle wear will be permitted. During the two study periods, subjects will wear each of two lens types (ACUVUE OASYS® with HYDRACLEAR® PLUS, ULTRA™ with MoistureSeal™ Technology) for 4 weeks bilaterally (randomized order). There will be a 7 day minimum wash out requirement prior to V6 (dispense Lens 2). Subjects will be allowed to wear their own lenses during the washout except for the last 24 hours prior to dispensing of lens type 2. Subjects will be masked to the lens type during the two treatment periods. Due to the different replacement schedules for ACUVUE OASYS® with HYDRACLEAR® PLUS (2 weeks) and ULTRA™ with MoistureSeal™ Technology (4 weeks) CLs, subjects wearing ACUVUE OASYS® will have their lenses replaced with a fresh pair at the Day 14 visit while subjects wearing Ultra® will be re-dispensed the same lenses at the Day 14 visit. Lens replacement will be handled by study personnel; subjects will not be aware if lenses will have been replaced at either the Day 14 visits in lens wearing phase 1 (V4) or phase 2 (V8).

There will be a total of 9 study visits. Subjects will spend a total of 13 hours at the CCLR, with visit-specific durations as outlined below:

- Visit 1 – screening (2 hrs)
- Visit 2 – dispense lens type 1 (1 hr)
- Visit 3 – Day 1 follow-up with lens type 1 (1.5 hrs)
- Visit 4 – Day 14 follow-up with lens type 1 (1.5 hrs)
- Visit 5 – Day 28 follow-up with lens type 1 (1.5 hrs)
- Visit 6 – dispense lens type 2 (1 hr)
- Visit 7 – Day 1 follow-up with lens type 2 (1.5 hrs)
- Visit 8 – Day 14 follow-up with lens type 2 (1.5 hrs)
- Visit 9 – Day 28 follow-up with lens type 2 (1.5 hrs)

[figure not shown]

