10	Lens Fit Assessment	
Evaluate and grade lens centration, primary gaze movement, upgaze movement and tightness (push-up test).
 
An unacceptable lens fit will be any one or more of the following:
 
 • presence of limbal exposure (appearance of clear cornea) in any gaze • presence of edge lift • presence of unacceptable movement (excessive or insufficient) in all three movement categories (primary gaze, upgaze, and push-up). 
Note: If either lens is deemed unacceptable, the subject will not be able continue participation in the study (Section 16.2).
	Lens Fit Assessment
11	Lens Surface Evaluation	Grading Scale (Section 16.2) will be used to grade the front and back surface deposits.	Debris and Deposits
12	Distance and Near logMAR HCVA and LCVA	The subject's distance and near logMAR visual acuity will be determined with high (HCVA) and low contrast (LCVA) letter charts with the study lenses. The acuity will be recorded to the nearest letter for OD, OS and OU. See section 16.2.	Distance and Near logMAR HCVA and LCVA
13	Near Contrast Sensitivity	The subject's contrast sensitivity will be tested at near using Mars Letter Contrast Sensitivity Test Cards with the study lenses. The subject's contrast sensitivity will be recorded to the nearest letter for OU, in 0.04 log unit incremental steps. See Section 16.2.	Near Contrast Sensitivity
14	Time to haze	The subject's "time to haze" will be determined at 1m distance with the study lenses. First, the subject's psychophysical contrast threshold will be determined using a computerized chart. "Time to haze" will then be measured at 1 level above threshold. Directly after, the subject's required "time to clear" will be determined by counting blinks until the subject has cleared the haze. See Section 16.2.	Time to haze
15	Lens Removal	
Study lenses are removed from the eyes and are disposed of at the CCLR.
 
In case of a product defect (e.g. lens edge tear), study lens (es) will be retained and returned to the sponsor, and a product complaint form will be completed in BioClinica. In case of a corneal adverse event, study lens(es) will be retained and analyzed at the CCLR.
	Lens Removal
16	Efron Biomicroscopy	The Efron slit lamp classification scale will be used to grade the findings. This includes corneal and conjunctival staining measurements with fluorescein (Section 16.2).	Biomicroscopy

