4.9 ACCOUNTABILITY PROCEDURES FOR STUDY ARTICLES

Johnson & Johnson Vision Care, Inc. will provide the Investigator with sufficient quantities of study articles and supplies to complete the investigation. The Investigator is asked to retain all lens shipment documentation for the test article accountability records. The Investigator may provide the subject additional lenses in the event a lens is damaged or lost between visits. Lens dispensation will be recorded on lens accountability logs, as well as, in the EDC system.

Test articles must be kept in a lockable room, accessible only to those assigned by the Investigator for dispensing. All investigational products must be accounted. This includes 1) what was dispensed for the subject to wear out of the office or issued for the subject to replace appropriately between visits and 2) the number and reason for unplanned replacements. The Investigator may delegate this activity to an authorized study site staff member on the Delegation Log.

Worn study lenses will be collected at the Day 14 (ACUVUE OASYS®) and Day 28 visit (both lens types) and disposed of at the site as per local guidelines. Following final reconciliation of test articles, the Investigator will **destroy on site the unused lenses per local guidelines.**

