5.1 WITHDRAWAL CRITERIA

A subject will be withdrawn from the study for any of the following reasons:

- Lost to follow-up
- Withdrawal of consent
- Death
- Discontinuation of study treatment as a result of the investigator's belief that for safety reasons (e.g., adverse event) it is in the best interest of the subject to stop treatment.
- The subject becomes pregnant.
- Non-compliance to the protocol.

For discontinued subjects, the Investigator will:

- Complete the "last" Follow-up Visit form (scheduled or unscheduled)
- Complete the Final Evaluation form, indicating the reason that the subject was discontinued from the study
- Record the spherocylindrical refraction with best corrected distance visual acuity
- Collect used study lenses and test articles (worn or brought to the visit) from the subject and discard them
- Collect all unused study lenses and test articles from the subject

Subjects becoming pregnant during the study will be discontinued. Once discontinued, pregnant subjects and their fetuses will not be monitored for study related purposes. However, these data will not be collected as part of the clinical study database. Pregnant subjects are not discontinued from contact lens or solution related studies for safety concerns, but due to general concerns relating to pregnancy and contact lens use. Specifically, pregnant women are discontinued due to fluctuations in refractive error and/or visual acuity that occur secondary to systemic hormonal changes, and not due to unforeseen health risks to the mother or fetus.

In cases where a subject is lost to follow-up, every possible effort must be made to contact the subject and determine the reason for discontinuation / withdrawal. The measures taken to follow up must be documented including two written attempts and a certified letter as the final attempt.

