9.1 STATISTICAL METHODS TO BE EMPLOYED

This method is a general outline of the statistical methods that will be implemented in this clinical trial. For more details, refer to the stand-alone Statistical Analysis Plan (SAP) of this clinical study.

Cohort Populations:

CR-5816 Protocol v7.0, Amendment 6.0

- The analysis population will include subjects who have successfully completed all study visits without a protocol deviation documented as impacting the unbiased assessment of the hypotheses
- The safety population will include all randomized subjects who have successfully tried at least one study lens

Statistical Considerations:

Statistical programming and analyses will be performed using SAS (SAS Institute, Cary, NC) version 9.4 or higher. Throughout the analysis of the data, the results of each eye will be used when available for summarization and statistical analysis.

Summary tables (Descriptive statistics and/or frequency tables) will be reported at baseline and each post fit time period for all efficacy and safety variables for each subject/eye by study lens type (as appropriate) for both the completed and discontinued subjects. Continuous variables will be summarized with descriptive statistics (number non-missing (n), mean, standard deviation (SD), median, minimum and maximum). Frequency count and percentage of subjects or eyes within each category will be provided for categorical data. Unscheduled visits will be summarized separately if applicable.

Summaries will be presented by study article type (Test OR Control). The denominator for percentages of counts will be the same for each visit on the summary tables and will equal the final number of subjects or eyes in the group under consideration. Unscheduled visits will be summarized separately and excluded from the analysis.

Analysis Population Sets:

Primary and secondary analyses will be performed on all randomized subjects who completed the study and did not substantially deviate from the protocol as determined by the trial cohort review committee prior to database hard lock (Per-protocol population). Justification for excluding subjects with protocol deviations will be documented in a memo to file.

Primary Analysis:

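### A Day 28 misfit of lens 1 at V5 ends study participation, although lens 1 wear is already over and lens 2 has its own fit check at V6

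*Protocol*

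**What the plan says.** Protocol 4.7.1, Visit 5, step 10 grades the fit of the lens 1 pair on Day 28. Limbal exposure, edge lift, or unacceptable movement in all three movement categories makes the fit unacceptable. The consequence is unconditional: "If either lens is deemed unacceptable, the subject will not be able continue participation in the study (Section 16.2"). Only the lens 1 pair is on the eyes at V5, so the phrase refers to the right or left lens of that pair.

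Step 15 of the same visit reads: "Study lenses are removed from the eyes and are disposed of at the CCLR". Section 4.9 agrees: "Worn study lenses will be collected at the Day 14 (ACUVUE OASYS®) and Day 28 visit (both lens types"). Section 4.4 then requires a break before the second lens: "There will be a 7 day minimum wash out requirement prior to V6 (dispense Lens 2"). At V6 the subject receives the other lens type, and step 11 of that visit repeats the fit criteria and the same consequence for it.

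Section 5.1 lists six reasons for withdrawal, and lens fit is not among them. One of the six covers the investigator's belief that "for safety reasons (e.g., adverse event) it is in the best interest of the subject to stop treatment". On the analysis set, 9.1 says: "Primary and secondary analyses will be performed on all randomized subjects who completed the study", further limited to those without a substantial protocol deviation.

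**The concern.** A rule that stops participation for poor fit makes sense while the graded lens is still to be worn. At V5 none of that wear remains, so the rule cannot protect the subject from lens 1. It does not test lens 2 either, which is a different product (senofilcon A, base curve 8.4, against samfilcon A, base curve 8.5; section 2.1).

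Its only effect is to withhold the second period. In a 2x2 crossover analysed on completers, that removes the subject from the lens comparison, including the lens 1 comfort ratings already given. The trigger is a post-randomization property of whichever lens was worn first. What is at stake is an exclusion that serves no purpose, plus the enrolment needed to replace the lost completer. An analysis plan cannot repair it, because the lens 2 data are never collected.

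**Working it through.** There is no stated figure to reproduce. The check sets the fit notes of 4.7.1 side by side and asks what each one still guards.

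| Visit | Step | Lens graded | Wear of that lens type still to come |
|---|---|---|---|
| V2 | 11 | lens 1 | yes |
| V3 | 9 | lens 1 | yes |
| V4 | 9 | lens 1 | yes (fresh ACUVUE OASYS pair, or the same ULTRA pair) |
| V5 | 10 | lens 1 | none |
| V6 | 11 | lens 2 | yes |
| V7 | 9 | lens 2 | yes |
| V8 | 9 | lens 2 | yes |
| V9 | 10 | lens 2 | none |

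Lens 1 passes four gates. Three guard further wear and the one at V5 does not. V9 is the same for lens 2, but there the study is ending anyway, so the note has practically no effect.

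**Is the V5 note needed for safety?** No. Section 5.1 already allows withdrawal for safety. Biomicroscopy is done at V5 step 16 and again at V6 step 4. V6 step 5 allows a second dispense visit if a temporary finding prevents fitting.

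**What happens to a subject stopped at V5?**
- Lens 2 is never worn, so the subject has not completed the study and is outside the set for the primary and secondary analyses (9.1).
- The subject remains in the safety population (8.1 and 9.1) and in the descriptive summaries, which 9.1 prepares "for both the completed and discontinued subjects".
- The Day 28 CLUE rating (V5 step 6) has already been given. The protocol does not fix how many lens 1 ratings leave the primary model. It is 2 if only the 2-week and 4-week ratings count, 3 with V3 step 5 added, and 4 if the second V4 administration (step 17) also counts.

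**Cost in enrolment.** Sections 2.6 and 9.4 describe the phase 1 data as already analysed, so a lost completer can be replaced only in phase 2. The synopsis says: "The study enrolment will be stopped after 50 additional phase 2 subjects complete the final visit". Inputs are the enrolment cap of 250, about 135 enrolled in phase 1, and 50 phase 2 completers:

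(250 − 135) / 50 = 115 / 50 = 2.3 enrolments per phase 2 completer.

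This is a planned ceiling, not an expected value. The corresponding phase 1 ratio, 135 / 80 = 1.7, describes a phase in which replacement is no longer possible.

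**How many subjects?** The protocol gives no Day 28 fit-failure rate, overall or by lens. Only failures that are new after the three earlier lens 1 gates count, which points to a small number, but no estimate is possible.

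**The case against.** The strongest reply is that this is repeated template text. The note stands at every visit with a study lens on the eye, including V9. V5 step 19 sends subjects to washout and V6 without a fit exception, and 5.1 does not support the note. The site may therefore never apply it at V5. That is plausible, but the visible rule is unconditional and a site that follows the visit table must apply it. Wording that staff are expected to ignore should be removed.

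Second, the lens-fitting procedure cited through Section 16.2 (Appendix B) is redacted and may say how a follow-up misfit is handled. This limit stands, and the point rests on the visible text.

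Third, a per-protocol comparison of comfort in well-fitted eyes is legitimate, and a lens that became unacceptable between Day 14 and Day 28 was worn poorly fitted for part of the rated period. That bears on whether the subject is evaluable, which the cohort review committee already decides under 9.1. It is no reason to withhold lens 2 before that decision.

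A reader might go further and infer that the rule biases the comparison in favour of one lens, because a misfit at Day 28 of period 1 costs the second period while the same misfit in period 2 costs almost nothing. The asymmetry is real. Without fit-failure rates by lens, however, the documents support neither a direction nor a size. Nor do they support reading the rule as a threat to the completer target, since phase 2 enrolment runs until 50 more subjects complete, provided the cap is not reached first. Nor does a stopped subject vanish from the report, given the safety population and the descriptive summaries.

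**Conclusion.** The point holds as a minor one. At V5 step 10 a fit failure of a lens whose wear is finished ends participation, protects nothing, and creates an avoidable post-randomization exclusion from the completers-only primary and secondary analyses. The number of subjects is unknown and probably small, and no wrong result or altered inference is shown. The conclusion assumes that the note is applied as written and that the redacted fitting procedure does not override it. The 2.3 ceiling further assumes that phase 1 enrolled about 135 and that the removed subject would otherwise have completed. This is a cheap improvement, not a defect that endangers the trial.

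**What to change.** At V5 step 10 keep the fit grading and replace the participation note with: *An unacceptable fit at this visit is recorded; the subject completes V5 and proceeds to washout and the V6 fit check unless withdrawn for safety under 5.1.* Delete the same functionless note at V9 step 10. Leave V2 to V4 and V6 to V8 unchanged, because there the note guards further wear of the graded lens type. Whether a subject with a recorded V5 misfit enters the per-protocol set stays with the cohort review committee under 9.1.

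No visit, procedure or data item is added. The cost is a small protocol amendment submitted to the IEC/IRB (12.3). It also leaves a minor difference in the continuation rule between phase 1 and the remaining phase 2 subjects, introduced after the interim data were reviewed, which the study report should note.
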